## 1. BACKGROUND

Coronary artery disease (CAD) is considered one of the main causes of morbidity and mortality worldwide and in Jordan. One of the major risk factors that contributes to the development and progression of CAD is dyslipidemia(1). According to the World Health Organization (WHO), an estimated 17.9 million patients died in 2016 because of cardiovascular diseases, of which more than 80.0% of the deaths were due to stroke and myocardial infarction(2). A large number of clinical trials have reported the benefits of lowering LDL-C, in reducing the mortality rate among CAD patients(3), Based on that, the American College of Cardiology (ACC/AHA) published the 2019 blood cholesterol treatment guidelines to reduce atherosclerotic cardiovascular risk in adults. Which expands the role of LDL-C targets. It also specifies the importance of percentage reduction in LDL-C when prescribing high- or moderate-intensity statins as well as the medication's adherence by LDL-C testing and the efficacy of statin therapy. Furthermore, it highlights the importance of adding PCSK9 inhibitor therapy after receiving the maximum tolerated statin therapy and ezetimibe to achieve LDL-C < 70 mg/dl or non-HDL-C < 100 mg/dl for patients in each of the 4 statin benefit groups with atherosclerosis cardiovascular disease (ASCVD) with or without comorbidities (4)

The objective of physician continuing medical education (CME) is to help them keep abreast of advances in patient care, to accept new more-beneficial care, and discontinue use of existing lower-benefit diagnostic and therapeutic interventions(5), one of the medical barriers prevent patients from achieving goals, contributing to the perceived gap between the updated guidelines and daily clinical practice (6).

The present study aims to examine the trend of physician and their patients in measuring lipid profile and modifying the lipid lowering agents, then show the prevalence of patients, those with known ASCVD, who have LDL-C more than or equal to 70 mg/dl during using their statin treatment plan and compare this percentage with patients' healthcare provider specialty, and to study the impact of continuous medical education for Health care providers on lipid lowering therapy target goals achievement.

## 2. AIM OF STUDY / RESEARCH QUESTIONS

1. To examine the trend of physician and their patients in measuring lipid profile and modifying the lipid lowering agents in Jordan.
2. Measure the prevalence of patients, those with known ASCVD, who have LDL-C more than or equal to 70 mg/dl during using their statin treatment plan
3. To study the impact of continuous medical education for Health care providers on lipid lowering therapy target goals achievement.

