#### 4. STUDY SETTING/LOCATION

The study will be conducted in Jordanian Cardiologist, Internist and General Physicians Clinics among Jordan from South to North.

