#### 5. STUDY POPULATION AND SETTING:

- Target around 500 subjects in each group.
- Written informed consent was obtained from all study participants.
- Participation in the study was voluntary and the participants could quit at any time. Data confidentiality was guaranteed by the research team in JPM scientific office.
- Participation in the study is voluntary and no compensation will be paid to the subjects.

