#### 6. ELIGIBILITY CRITERIA

##### • Inclusion criteria:

- Adults more than or equal to 18 years old.
- Subject willing to sign the consent form and using a lipid lowering agent.
- Known ASCVD.
- ON statin for the past three months or more with LDL-C > 70mg/dl.

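### Requiring LDL-C > 70 mg/dl for entry fixes the aim 2 prevalence at 100% and its specialty comparison at zero at entry; the population of aim 1 also needs naming

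*Protocol*

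**What the plan says.** Aim 2 (Protocol, section 2) is to "Measure the prevalence of patients, those with known ASCVD, who have LDL-C more than or equal to 70 mg/dl" while on their statin plan. The last paragraph of the Background adds that this percentage will be compared by provider specialty; the sentence continues "healthcare provider specialty, and to study the impact of continuous medical education", which is aim 3.

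Aim 1 is "To examine the trend of physician and their patients in measuring lipid profile and modifying the lipid lowering agents in Jordan". It names no disease, treatment or LDL-C limit.

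The inclusion criteria in section 6 require adult age, consent, use of a lipid-lowering agent, known ASCVD, and "ON statin for the past three months or more with LDL-C > 70mg/dl". They make no distinction between aims. Section 5 gives the size as "Target around 500 subjects in each group". The design section calls the study prospective and interventional. No separate survey sample, screening log or other denominator for aims 1 and 2 appears in the text shown.

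**The concern.** A prevalence needs a denominator that contains patients on both sides of the threshold. The inclusion list removes one side before anyone is counted. If the plan is followed as written and aim 2 is read at entry, its result repeats the eligibility rule, and the specialty comparison cannot show a difference even if cardiologists, internists and general physicians differ widely. One of three stated aims then yields no information at entry. An analysis plan cannot repair this, because patients at or below 70 mg/dl were never sampled.

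The limits to known ASCVD and to statin use are not at issue, since aim 2 names both itself. Only the LDL-C clause is. That clause suits aim 3, which asks whether treatment goals are reached after education of the providers.

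Aim 1 is touched more lightly. Testing and treatment changes can be followed in enrolled patients, but the result describes a narrower group than the aim's wording suggests.

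**Working it through.** **Inputs, all from the protocol**
- Event counted in aim 2: LDL-C ≥ 70 mg/dl (section 2).
- Entry condition: LDL-C > 70 mg/dl, with known ASCVD and statin for at least three months (section 6).
- Size: about 500 per group (section 5). The text shown gives no rate or precision behind this number, so there is no figure to reproduce, and the result below does not depend on it.

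**Step 1: aim 2 at entry.** The set {LDL-C > 70} lies inside {LDL-C ≥ 70}. Therefore P(LDL-C ≥ 70 | LDL-C > 70) = 1 for any LDL-C distribution. In a group of 500 this is 500/500 = 100%, with 0 patients at or below 70. As a check, three assumed normal distributions were simulated, with unrestricted prevalences of 50.1%, 69.2% and 80.4%. After the entry condition was applied, the prevalence was 100% each time.

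A patient at exactly 70 mg/dl counts as a case under aim 2 but cannot enter under section 6. The two signs should be reconciled, but this does not change the 100%.

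**Step 2: specialty comparison at entry.** Each specialty has 100%, so any difference is 100 − 100 = 0 percentage points, whatever the true rates.

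**Step 3: aim 2 after entry.** The proportion at or above 70 can fall during follow-up. Among patients who all started above 70, that fall is the share reaching goal. This is the aim 3 quantity, not the prevalence among statin-treated ASCVD patients.

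**Step 4: aim 1.** Let g be the share of statin-treated ASCVD patients at goal, and r_goal and r_above the rates of testing or treatment change at goal and above goal.
- All treated patients: g × r_goal + (1 − g) × r_above.
- Enrolled patients: r_above.
- Difference, enrolled minus all treated: g × (r_above − r_goal).

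The protocol gives neither g nor r_goal, and the design as written collects neither. The difference has no known size or sign, so no figure is assigned.

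**Step 5: what removing the clause for aim 2 would give.** The 95% half-width is 1.96 × √(p(1 − p)/n). The prevalences p are assumptions, not figures from the protocol.

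| Assumed p | n = 500 | n = 1000 |
|---|---|---|
| 0.5 | 4.4 points | 3.1 points |
| 0.8 | 3.5 points | 2.5 points |

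Here n is the number of patients with an LDL-C result. Precision within one specialty depends on how many of them that specialty contributes, which the protocol does not state.

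**The case against.** **Aim 2 names no time point.** It speaks of patients during their statin plan, so a proportion taken in follow-up is not excluded, and that proportion need be neither 100% nor equal across specialties. This stands as a reading of the text, and for that reason the 100% is claimed at entry only. It does not rescue the aim, because of step 3.

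**Unseen sections may define a sample.** Section numbering runs 1, 2, 4, 4, 5, 6, with an empty item 9 under the design heading. A data-collection section may not be shown. This also stands: the absence of a screening log is read with caution. The population and eligibility sections are shown, however, and they tie the LDL-C clause to the study as a whole.

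**Aim 1 is not shown to be wrong.** A reader might infer that aim 1 would give biased rates, or that rates in above-goal patients would be passed off as practice across the country. The documents do not support that:
- Reference to Jordan, and to "Jordanian Cardiologist, Internist and General Physicians Clinics among Jordan from South to North", can be read simply as location.
- The protocol makes no claim of representativeness.
- The Background phrase "adherence by LDL-C testing and the efficacy of statin therapy" summarises a guideline and does not define this study's population.
- The protocol does not say that a value above 70 itself prompts retesting.
- Aim 1 names no ASCVD or statin limit either, so the LDL-C clause is not its only unstated restriction.

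What remains for aim 1 is that its population should be named.

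**Conclusion.** The contradiction between aim 2 and the inclusion criteria holds with certainty at entry: prevalence 100% in every group and specialty, and a between-specialty difference of 0 points. It follows from the two thresholds alone and needs no assumption about LDL-C values, sample size or analysis method. It does assume that the inclusion list shown applies to aim 2, as its wording implies, and that no section outside the text shown supplies another denominator.

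For aim 1 the conclusion is limited to a mismatch between its unrestricted wording and an enrolled population of above-goal, statin-treated patients with known ASCVD. Testing and treatment changes after enrolment can still be estimated in that population. No bias is asserted.

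The sponsor should correct this before recruitment, or before reporting if recruitment is under way.

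**What to change.** **Preferred.** Apply LDL-C > 70 mg/dl only to the aim 3 cohort. Estimate aim 2 and its specialty comparison, and describe aim 1, on all consecutive screened patients with known ASCVD and statin for three months or more, and name that population in both aims. For each patient record provider specialty and LDL-C. Count patients with no LDL-C result separately, so that they neither vanish from the denominator nor pass as at goal. Report the prevalence with confidence intervals by specialty.

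The cost is a screening log with some chart abstraction, plus ethics or consent cover for patients who do not enter aim 3, since section 5 states "Written informed consent was obtained from all study participants". The aim 3 target of about 500 per group does not change. The number logged depends on the unknown share at goal, so precision by specialty cannot be promised in advance.

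**If no such log is kept.** Restate aim 1 as limited to statin-treated patients with known ASCVD and LDL-C > 70 mg/dl, and remove the aim 2 prevalence and its specialty comparison. This costs only wording, but aim 2 is lost and nothing is learned about patients at goal.

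**If a section not shown already defines such a sample.** Cite it in section 2 as the aim 2 denominator; nothing further is then needed for aim 2.

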## 4. STUDY DESIGN:

This is a prospective interventional multicentral study including several clinics of Cardiologist, Internist and General Physicians, in Jordan.

9. Other notes:

#### 4. STUDY SETTING/LOCATION

The study will be conducted in Jordanian Cardiologist, Internist and General Physicians Clinics among Jordan from South to North.

#### 5. STUDY POPULATION AND SETTING:

- Target around 500 subjects in each group.
- Written informed consent was obtained from all study participants.
- Participation in the study was voluntary and the participants could quit at any time. Data confidentiality was guaranteed by the research team in JPM scientific office.
- Participation in the study is voluntary and no compensation will be paid to the subjects.

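### Does a target of about 500 patients per group, with no number of physicians, undermine a study of education given to providers?

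*Protocol*

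**What the plan says.** Section 2 of the protocol gives as its third aim: "To study the impact of continuous medical education for Health care providers on lipid lowering therapy target goals achievement". The intervention therefore acts on the provider, while the outcome, LDL-C against its target, is read on each patient. The Background section adds a second provider-level contrast, to "compare this percentage with patients' healthcare provider specialty".

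The only statement of size is in section 5, Study population and setting: "Target around 500 subjects in each group". The Study design section describes a multicentre study "including several clinics of Cardiologist, Internist and General Physicians, in Jordan", and the Study setting section places it in "Cardiologist, Internist and General Physicians Clinics among Jordan from South to North".

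The visible text gives no definition of the groups, no count of physicians or clinics, and no maximum per physician. It also gives no alpha, power, expected rates or basis for the 500.

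**The concern.** Patients of one physician tend to be treated alike, so their outcomes are correlated. When a provider-level intervention is compared between different providers, the amount of information depends on how many providers there are as well as how many patients. Because the target is set in patients alone, 500 patients from a handful of prescribers would satisfy it.

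At stake is the precision of the education effect. Recruitment concentrated in few prescribers could leave an estimate too imprecise to be useful. A clustered analysis would report that imprecision honestly but could not recover the lost information. The undefined groups add to the doubt, because the size of the loss depends on whether the groups share physicians.

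**Working it through.** **The plan's own figure.** The 500 cannot be reproduced, because the protocol gives no error rates, expected proportions, effect size or ICC. It therefore cannot be shown to be too small against any stated goal.

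**Inputs.** From the protocol: n = 500 per group. Assumed: ICC, patients per physician m, proportions near 50%, equal cluster sizes, and the correlation r between periods within a clinic.

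**Formulas.** The 95% half-width of a difference between two groups is 1.96 × √(2 × 0.25 / n_eff), with n_eff = 500 / DE. With independent patients, 1.96 × √(0.5/500) = 6.2 points. A normal quantile is used; with few clusters a t quantile would be wider.

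**(a) Parallel groups of different physicians.** DE = 1 + (m − 1) × ICC. For m = 50 and ICC 0.10, DE = 1 + 49 × 0.10 = 5.90, n_eff = 85 and the half-width is 15.1.

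| Patients per physician | Physicians per group | n_eff, ICC 0.02 to 0.10 | Half-width (points) |
|---|---|---|---|
| 50 | 10 | 253 to 85 | 8.7 to 15.1 |
| 20 | 25 | 362 to 172 | 7.3 to 10.6 |
| 10 | 50 | 424 to 263 | 6.7 to 8.5 |

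Over a wider range, 250 physicians at ICC 0.01 give n_eff 495 (a loss of 1%), and 5 physicians at ICC 0.10 give 46 (a loss of 91%).

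In terms of power, take an assumed 30% v 40% at goal, two-sided 0.05. Power is 91% with 500 independent patients per group. With 10 physicians per group it is 77.6%, 43.0% and 27.5% at ICC 0.01, 0.05 and 0.10.

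**(b) Before and after in the same clinics, different patients.** DE = 1 + (m − 1) × ICC − m × ICC × r. For m = 50, ICC 0.05 and r = 0.5, DE = 1 + 2.45 − 1.25 = 2.20.

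| Patients per clinic per period | n_eff at r = 0.5 / 0.8 / 1.0 (ICC 0.05) | Half-width (points) |
|---|---|---|
| 50 | 227 / 345 / 526 | 9.2 / 7.5 / 6.0 |
| 10 | 417 / 476 / 526 | 6.8 / 6.4 / 6.0 |

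At r = 1.0 the comparison is slightly more precise than one of independent patients.

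**(c) Same patients followed after the education.** The inclusion criteria admit only patients with LDL-C above 70 mg/dl, so this is also a natural reading. Attainment at entry is then essentially zero by eligibility, and a comparison of two independent proportions near 50% does not apply.

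**Specialty contrast.** For the same reason, the share with LDL-C at or above 70 mg/dl among enrolled patients is about 100% in every specialty at entry. That prevalence needs a wider denominator than the enrolled patients, so a precision calculation on a third of one group does not describe it.

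**The case for a change.** The strongest case for acting is that the number of physicians is a design fact. A mixed model or a small-sample correction can be left to an analysis plan, but clusters cannot be added once recruitment has ended. The nationwide setting suggests a wide spread but guarantees no number: about 10 physicians per group could cover three specialties and several regions, leaving about 3 per specialty. Stating a physician target would keep the patient total.

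Much of this stands. The omissions are real in the visible text, the arithmetic is sound under its assumptions, and concentrated recruitment in parallel groups would cost precision. What does not stand is the step from possible to likely. Nothing in the protocol points to 50 patients per physician, and its description of the sites points the other way.

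The text may also be incomplete. The Study design section is one sentence followed by an item numbered 9 with nothing under it, which may be the end of a list whose other items are not shown. Careless numbering is another explanation, since two sections carry the number 4.

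**Conclusion.** The concern does not call for a change. Depending on how the groups are defined and how recruitment spreads, the effect runs from no loss (half-width 6.0 points, before/after in the same clinics at r = 1.0) to more than a doubling (15.1 against 6.2, parallel groups with 10 physicians each at ICC 0.10). All inputs to that range other than the 500 are assumed. The protocol promises no power, precision or independence that its target would break, so following it is not shown to give a wrong result.

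What the concern asks for falls into two parts. Defining the groups, naming the physician as the clustering unit, and stating an effective sample size or a clustered analysis would write down details that an analyst or an analysis plan can supply. The one part that would alter the trial is a maximum per physician. At 10 patients each, about 500/10 = 50 physicians per group would have to be recruited and, where applicable, trained, against 500/50 = 10 at 50 patients each. That exchanges operational burden for precision. It is a judgement for the sponsor and not the correction of an error.

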#### 6. ELIGIBILITY CRITERIA

##### • Inclusion criteria:

- Adults more than or equal to 18 years old.
- Subject willing to sign the consent form and using a lipid lowering agent.
- Known ASCVD.
- ON statin for the past three months or more with LDL-C > 70mg/dl.

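### Aim 2 asks what share of known-ASCVD statin patients have LDL-C at or above 70 mg/dl, but the inclusion list admits only patients above 70, so enrolled subjects cannot supply that share or its comparison by specialty

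*Protocol*

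**What the plan says.** Section 2 of the protocol lists three aims. The first concerns practice: "To examine the trend of physician and their patients in measuring lipid profile" and changing lipid-lowering agents. The second is a prevalence: the share of patients with known ASCVD "who have LDL-C more than or equal to 70 mg/dl during using their statin treatment plan". The third is the "impact of continuous medical education for Health care providers on lipid lowering therapy target goals achievement".

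The last paragraph of section 1 (Background) repeats the second aim as a purpose of the study, to "show the prevalence of patients, those with known ASCVD" and LDL-C at or above the threshold, and extends it: the study will "compare this percentage with patients' healthcare provider specialty".

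Section 6 has the only inclusion list. Besides adult age, consent and use of a lipid-lowering agent, it requires known ASCVD and "ON statin for the past three months or more with LDL-C > 70mg/dl". Nothing limits the list to one of the three aims. Section 4 describes the design: "This is a prospective interventional multicentral study including several clinics of Cardiologist, Internist and General Physicians, in Jordan". Section 5 sets the size: "Target around 500 subjects in each group". The text at hand describes no separate prevalence sample, no screening log and no wider denominator.

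**The concern.** A prevalence needs a denominator containing both patients with the condition and patients without it. Here the condition is LDL-C at or above 70 mg/dl on a statin, and the entry rule removes everyone below that level. The enrolled subjects are the numerator of aim 2 with the rest of its denominator missing. The same holds within each provider specialty, so the planned comparison of specialties has nothing to compare at entry.

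One of three stated aims, and the specialty comparison attached to it, would get an answer fixed by the eligibility rule. A reader could take the published percentage as a description of lipid control in Jordan when it describes only who was let into the study. No analysis plan can repair this after the fact if patients at or below 70 mg/dl were not recorded.

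**Working it through.** **Inputs from the protocol**

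| Item | Where | Value |
|---|---|---|
| Population of aim 2 | section 2, item 2 | known ASCVD, on statin |
| Condition counted | section 2, item 2 | LDL-C ≥ 70 mg/dl |
| Entry rule | section 6 | known ASCVD, statin for three months or more, LDL-C > 70 mg/dl |
| Specialties compared | sections 1 and 4 | cardiologists, internists, general physicians |
| Size | section 5 | about 500 per group |

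The figure of 500 cannot be reproduced, since the protocol gives no rate, precision, alpha or power with it. It does not matter here, because the problem does not depend on sample size.

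**Step 1: share at entry.** Every LDL-C above 70 is also at or above 70, so

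P(LDL-C ≥ 70 | LDL-C > 70) = 1.

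The share is 100% in each specialty and the difference between any two specialties is 100% − 100% = 0. If the true prevalence is p, the enrolled share overstates it by 1 − p: for example 1 − 0.60 = 40 points, or 1 − 0.90 = 10 points.

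**Step 2: share at a later visit.** The study is prospective and aim 2 refers to the period of statin use, so the percentage might be meant for a later measurement. The protocol gives neither the true prevalence nor the within-person correlation of repeat LDL-C, so what follows is illustration only. Assume that entry and later LDL-C are bivariate normal on a suitable scale, with the same marginal distribution at both times, correlation r and no change in treatment. With c = Φ⁻¹(1 − p),

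P(later ≥ 70 | entry > 70) = Φ₂(−c, −c; r) / p.

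| True p | r = 0.5 | r = 0.7 | r = 0.9 |
|---|---|---|---|
| 60% | 73.2% | 79.6% | 88.4% |
| 80% | 85.9% | 89.1% | 93.7% |
| 90% | 92.5% | 94.1% | 96.5% |

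For two specialties with true values of 60% and 80%, a gap of 20 points, the later gap would be:

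- r = 0.5: 85.9 − 73.2 = 12.7 points
- r = 0.7: 89.1 − 79.6 = 9.5 points
- r = 0.9: 93.7 − 88.4 = 5.3 points

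Under these assumptions the later share is too high and the specialty gap too small. If the education changes treatment, the later share could also fall below the true prevalence. In either case it does not identify the quantity in aim 2.

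**Step 3: the boundary.** A patient at exactly 70 mg/dl counts as a case in section 2 but is not eligible under section 6. This is minor, and steps 1 and 2 are unaffected by which sign is used.

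**The case against.** The strongest reply is that the conclusion rests on what a short document does not say. Section 6 restricts who enters the study, not who is screened. The clinics may keep a log of all statin patients seen, and aim 1, which asks whether lipids are measured at all, suggests an interest in patients beyond those already known to exceed 70 mg/dl. That is possible, but the protocol states no such denominator, so the aims and the entry rule conflict as written. What stands is that the defect is confined to enrolled subjects and disappears if a wider denominator is defined and recorded.

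A second reply is that later percentages by specialty need not be equal and can be informative. That is right: among patients who start above goal they compare goal attainment, which is close to aim 3. They are not the prevalence of aim 2. It is also fair that the direction of the error at follow-up is known only if treatment does not change, and that the assumed prevalences have no support in the document. The illustration shows scale; the argument does not need it.

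Third, clinic records might still supply the missing patients, so the loss need not be permanent. It becomes so only if those records do not hold LDL-C and provider specialty for patients at or below the threshold.

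Finally, aim 3 is compatible with the entry rule and is not touched by this point, and the protocol names no primary aim. That limits the reach of the problem, but one of three aims still cannot be answered.

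**Conclusion.** The concern holds and should be corrected before the study reports on aim 2. From the text alone, the share with LDL-C at or above 70 mg/dl among subjects at entry is 100% in every specialty and the difference between specialties is zero. This rests on no numerical assumption, only on section 6 being the inclusion list for the whole study, which is how it reads. Taking the percentage at a later visit does not recover the prevalence. With assumed true values of 60% to 90%, correlation 0.5 to 0.9 and no change in treatment, the later share would run from 73% to 88% for a true 60% and from 92% to 97% for a true 90%. This is a contradiction between the stated aims and the stated eligibility, not a detail left to the analysis plan.

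**What to change.** Reconcile sections 1, 2 and 6 of the protocol:

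1. Define the denominator for aim 2 as consecutive adults with known ASCVD, on a statin for at least three months, seen at the participating clinics, regardless of LDL-C. For each, log provider specialty and LDL-C, or that none is available. Report the percentage at or above 70 mg/dl among those measured, overall and by specialty, with the number unmeasured beside it, since measurement is the subject of aim 1. Consecutive sampling is the cleanest choice; the essential part is a stated denominator not selected on LDL-C.
2. State that the LDL-C entry criterion applies only to the education cohort of aim 3, if that is the intention.
3. Use the same boundary sign in sections 2 and 6.
4. If no such denominator will be recorded, drop aim 2 and its specialty comparison.

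The cost is protocol wording, short records for patients who do not meet the LDL-C criterion, and consent or waiver wording for them. The number of extra records per 500 patients at or above 70 is 500/p − 500, where p is an assumed prevalence: 333 at 60%, 167 at 75% and 56 at 90%. If p were as low as 30% it would be about 1,167. These are lower bounds, because refusals, exclusions and unmeasured patients add to them. Section 5 mixes past and future tense; if enrolment has already taken place, the denominator would have to come from clinic records, or option 4 applies.
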